#### 4.7 Removal of Subjects from Study Treatment and/or Study as a Whole

Patients can be taken off the study treatment and/or study as a whole at any time at their own request, or they may be withdrawn from study treatment at the discretion of the investigator for safety, behavioral or administrative reasons. The reason(s) for discontinuation from study treatment must be clearly documented on the appropriate eCRF and may include:

- Patient voluntarily withdraws from treatment (follow-up permitted)
- Patient withdraws consent (no follow-up permitted)
- Patient is unable to comply with protocol requirements
- Patient demonstrates disease progression

- Patient experiences unacceptable toxicity
  - See section on dose modifications: Treatment delay of > 4 weeks due to treatment related toxicities.
  - Protracted (>2 weeks) medically concerning grade 2 cardiac, pulmonary, renal, gastrointestinal, skin, or CNS toxicities.
- Grade  $\geq$  3 infusion reaction
- Treating physician determines that continuation on the study would not be in the patient's best interest
- Subject is determined to have met one or more of the exclusion criteria for study participation at study entry and continuing investigational therapy might constitute a safety risk
- Patient becomes pregnant or wants to become pregnant
- Patient develops a second malignancy that requires treatment which would interfere with this study
- Patient becomes lost to follow-up (LTF)
- Initiation of alternative anticancer therapy including another investigational agent
- Confirmation of PD and investigator determination that the subject is no longer benefiting from treatment with MEDI4736

#### 4.8 Patient Replacement/ Addition

- Any patient who is consented but does not receive at least one dose of investigational drug will be replaced.
- Any patient who withdraws their consent or otherwise discontinues study for any reason prior to undergoing surgery, will be considered as an early discontinuation, and another patient may be added as necessary.
# 5.0 STUDY PROCEDURES

## 5.1 Pre-Surgery & Surgery

Assessment/Activity	Screening & Baseline 	14 days (+/- 3 d) prior to surgery	Within 7 days prior to Surgery	Day of surgery	Within 72 hours Post- surgery
Informed Consent 	Х				
Review of eligibility criteria	Х				
Medical History	Х				
Concomitant Medications	Х		Х	Х	Х
Neurologic and Physical Exam 	Х		Х		Х
KPS	Х		Х		
Serum or Urine Pregnancy Test	Х				
Brain MRI or CT with contrast 	Х				$X^4$
CBC with diff & clinical chemistry 	Х	X	Х		
Magnesium and Phosphorus	Х	X	Х		
Thyroid testing 	Х				
PTT/PT/INR 	Х				
12-lead ECG 	Х				
Urinalysis with micro	Х				
Creatinine Clearance	Х				
Hepatitis serologies 	Х				
Toxicity assessment	Х			Х	Х
1 st Dose Study Treatment 		X 			
Archival Tissue for research 	X				
Fresh Tissue for research				X 	
Blood for research 		X		X	

 Includes vital signs (pulse, temperature, blood pressure, & weight). Height required at baseline only. On the first day of treatment, vital signs will be measured within an hour prior to start of initial study drug administration, at 30 minutes during the infusion (± 5 minutes), at the end of infusion (+ 5 minutes), and at 30 and 60 minutes (± 5 minutes each) post-infusion. If the infusion takes longer than 60 minutes, blood pressure and pulse measurements should follow the principles described here or more frequently if clinically indicated.

 Baseline procedures (with the exception of informed consent and archival tissue) must be obtained within 14 days of registration. The CBC and chemistries will be repeated within 72 hours of 1 st dose of study treatment if baseline tests were more than 7 days prior to dosing.

 Informed consent should be obtained within 28 days prior to registration.

- IRB #: STU00202283-MOD0025 Approved by NU IRB for use on or after 2/8/2019 through 1/6/2020. The baseline MRI can be up to 21 days prior to registration. The post-surgical MRI of brain should be done within 72 hours after surgery.
-  Twelve-lead ECGs will be obtained after the subject has been resting in a supine position for at least 5 minutes. ECG will be in triplicate (taken 2-5 minutes apart).
-  Patients will receive one dose of tremelimumab 75 mg (if on Arm 1), MEDI4736 750 mg (if on Arm 2) or the combination of both (if on Arm 3) approximately 2 weeks (14 days +/- 7 days) before surgery.
-  Tumor from prior surgeries will be requested on all patients. Tissue will be analyzed in the [name] Laboratory. Please refer to Section 9.3 and laboratory manual for details.
-  Blood samples will be collected for various research tests at 1 st pre-operative treatment, day of surgery, C1D1 and at each adjuvant treatment imaging visits (i.e. every 2 cycles or 8 weeks):
  - a) 10ml blood in one 10ml Sodium heparin tube: To be collected and processed by the [name] lab for peripheral blood lymphocytes (PBLs).
  - b)8m (2x4ml) blood in two 5ml EDTA (purple top) tubes: To be collected and processed by the [name] lab for gene expression profile using mononuclear cells.
  - c) 10ml blood in one 10ml red top tube: To be collected and processed by the [name] lab for analysis of tryptophan catabolites and cytokines.

Please refer to section 9.0 and laboratory manual for more details

 Chemistries should include electrolytes, calcium, , albumin, alkaline phosphatase, bilirubin (total), SGPT(ALT), SGOT(AST), serum creatinine, and BUN.

 TSH, T4, T3

 Required at baseline only but may be repeated as clinically indicated thereafter.

 Includes hepatitis A antibody, hepatitis B (HBsAg reactive), and Hepatitis C (HCV RNA [qualitative] detection).

 Please refer to Section 9.1 and the laboratory manual for details.

Time Period	Adjuvant Treatment 		Off Treatment			
Assessment/Activity	Cycle 1 Day 1  (+/- 2d)	Cycle 2 Day 1 (+/- 2d)	Cycle 3+ Day 1 (+/- 2d)	Treatment Discontinuation	90 Days Post Last Dose (+/- 7d)	Follow-up 
Concomitant medications	X	X	X			
Toxicity assessment	Х	Х	X	X	X	
Neurological exam and KPS 	Х	X	X	Х	Х	
Vital signs & weight 	X	X	X			
CBC with diff 	X		X	X	Х	
Comprehensive Chemistry Panel	X	X	X	X	Х	
Thyroid Function Tests 	X		X	X	Х	
ECG 	X			X		
Tumor Imaging (MRI/CT)	X 		X 	X 		
Tremelimumab monotherapy 	Х	X	X			
MEDI4736 monotherapy 	X	X	X			
Combination therapy 	X	X	X 			
Research tissue		X 	·			·
Research blood 	X		X 			
Survival status						X

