#### Pancreatitis

Immune-mediated pancreatitis, an important potential risk, is an inflammatory condition of the pancreas that typically manifests initially as asymptomatic elevations of amylase and lipase in patients treated with immune checkpoint inhibitors. Clinical presentation frequently includes low-grade abdominal pain with accompanying fever and malaise  Biopsies showed diffuse T-cell infiltrate consistent with immune- mediated pancreatitis {Weber, 2012}. Across the clinical development program for ipilimumab, immune-mediated pancreatitis has been reported in  $\leq 1\%$  ito 3% of patients (Yervoy, 2015). In monotherapy clinical studies of anti-PD-1 agents in melanoma, clinically significant immune-mediated pancreatitis was reported in < 1% of treated patients (Keytruda, 2015; Opdivo, 2015). Grade 3 or 4 treatment-related increased lipase was reported in 2% to 5% and increased amylase in < 10% of patients (Opdivo, 2015). In nivolumab and ipilimumab combination therapy studies, Grade 3 or 4 elevations in lipase and amylase were reported, respectively, in 16% and 5% of renal cell carcinoma patients, and 8% and 4% of NSCLC patients . Subjects should be monitored for signs and symptoms of pancreatitis including Grade 3 or 4 elevations in lipase and/or amylase. For Grade 3 and above asymptomatic amylase or lipase levels hold study drug/regimen and if complete work up shows no evidence of pancreatitis, may continue or resume study drug/regimen. In ongoing sponsored studies with MEDI4736 and

tremelimumab combination therapy, cumulatively, 4 serious events that occurred in 3 subjects (pancreatitis in 1 subject, pancreatitis acute in 1 subject, and amylase increased and lipase increased in 1 subject) have been assessed by the investigator as related to MEDI4736 and tremelimumab combination therapy.

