#### MEDI4736 and tremelimumab

The safety profile of MEDI4736 and tremelimumab combination therapy in the 102 subjects with advanced NSCLC in Study D4190C00006 is generally consistent with that observed across 177 subjects treated with MEDI4736 and tremelimumab combination therapy (not including subjects treated with blinded investigational product). As of 15Apr2015, 95 of 102 subjects (93.1%) reported at least 1 AE. All subjects in the tremelimumab 3 and 10 mg/kg dose cohorts experienced AEs; subjects in the

IRB #: STU00202283-MOD0025 Approved by NU IRB for use on or after 2/8/2019 through 1/6/2020. MEDI4736 20 mg/kg and tremelimumab 1 mg/kg Q4W cohort experienced the lowest AE rate (77.8%). Treatment-related AEs were reported in 74 of 102 subjects (72.6%), with events occurring in > 10% of subjects being diarrhea (27.5%), fatigue (22.5%), increased amylase and pruritus (14.7% each), rash (12.7%), colitis (11.8%), and increased lipase (10.8%). Treatment-related  $\geq$  Grade 3 AEs reported in  $\geq$  5% of subjects were colitis (8.8%), diarrhea (7.8%), and increased lipase (5.9%). Five subjects reported treatmentrelated Grade 4 events (sepsis, increased ALT, and increased AST in 1 subject; increased amylase in 2 subjects; myasthenia gravis in 1 subject; and pericardial effusion in 1 subject) and 2 subjects had treatment-related Grade 5 events (polymyositis and an uncoded event of neuromuscular disorder [VT]); the Grade 4 event of myasthenia gravis and Grade 5 polymyositis occurred in 1 subject. There were 2 subjects (both in the MEDI4736 20 mg/kg + tremelimumab 3 mg/kg Q4W cohort) with dose-limiting toxicities (DLTs): 1 subject with Grade 3 increased AST, and 1 subject with Grade 3 increased amylase and Grade 4 increased lipase. Fifty-six subjects (54.9%) reported SAEs, with events occurring in > 5% of subjects being colitis (9.8%) and diarrhea (7.8%). Thirty-six subjects (35.3%) experienced treatment-related SAEs. Twenty-seven subjects (26.5%) permanently discontinued treatment due to AEs. Treatment-related AEs resulting in discontinuation in  $\geq$  2 subjects were colitis (7 subjects), pneumonitis (5 subjects), diarrhea (3 subjects), and increased AST (2 subjects).

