can be resumed once event stabilizes to         Grade ≤1 after completion of steroid         taper. Patients with endocrinopathies who         may require prolonged or continued         steroid replacement can be retreated with         study drug/study regimen on the         following conditions:         1. The event stabilizes and is         controlled.         2. The patient is clinically         stable as per Investigator         or treating physician's         clinical judgement.         3. Doses of prednisone are at         ≤10 mg/day or equivalent.         Grade 3: Depending on the individual toxicity,         study drug/study regimen may be         permanently discontinue study         drug/study regimen. Note: For Grade ≥3         asymptomatic amylase or lipase levels,         hold study drug/study regimen, and if         complete work up shows no evidence of         pancreatitis, study drug/study regimen         may be continued or resumed. Note:         Study drug/study regimen should be         permanently discontinued in Grade 3         events with high likelihood for morbidity         and/or mortality – e.g., myocarditis, or         other similar events even if they are not         currently noted in the guidelines. </td 
 
e.g infliximab(also refer to individual sections of the imAEs for specific type of immunosuppressive) should be considered for events not responding to systemic steroids. Progression to use of more potent immunosuppressives should proceed more rapidly in events with high likelihood for morbidity and/or mortality – e.g., myocarditis, or other similar events even if they are not currently noted in the guidelines – when these events are not responding to systemic steroids.
 
With long-term steroid and other immunosuppressive use, consider need for Pneumocystis jirovecii pneumonia (PJP, formerly known as Pneumocystis carinti pneumonia) prophylaxis, gastrointestinal protection, and glucose monitoring.
 
Discontinuation of study drug/study regimen is not mandated for Grade 3/Grade 4 inflammatory reactions attributed to local tumor response (e.g., inflammatory reaction at sites of metastatic disease and lymph nodes). Continuation of study drug/study regimen in this situation should be based upon a benefit-risk analysis for that patient.
 
	
 
e.g infliximab(also refer to individual sections of the imAEs for specific type of immunosuppressive) should be considered for events not responding to systemic steroids. Progression to use of more potent immunosuppressives should proceed more rapidly in events with high likelihood for morbidity and/or mortality – e.g., myocarditis, or other similar events even if they are not currently noted in the guidelines – when these events are not responding to systemic steroids.
 
With long-term steroid and other immunosuppressive use, consider need for Pneumocystis jirovecii pneumonia (PJP, formerly known as Pneumocystis carinti pneumonia) prophylaxis, gastrointestinal protection, and glucose monitoring.
 
Discontinuation of study drug/study regimen is not mandated for Grade 3/Grade 4 inflammatory reactions attributed to local tumor response (e.g., inflammatory reaction at sites of metastatic disease and lymph nodes). Continuation of study drug/study regimen in this situation should be based upon a benefit-risk analysis for that patient.
 

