	For Grade 4:	NCCN guidelines for treatment of cancer-related infections [Category 2B recommendation]). a
	Permanently discontinue study	- Consider, as necessary, discussing with study physic
	drug/study regimen.	

Endocrinopathy	Any Grade	General Guidance	For Any Grade:
(e.g., hyperthyroidism, hypothyroidism, Type 1 diabetes mellitus, hypophysitis, hypopituitarism, and adrenal insufficiency; exocrine event of	(depending on the type of endocrinopathy, refer to NCI CTCAE v4.03 for defining the CTC grade/severity)		
 
Consider consulting an endocrinologist for endocrine events.
 
Consider, as necessary, discussing with study physician.
 
Monitor patients for signs and symptoms of endocrinopathies. Non-specific symptoms include headache, fatigue, behavior changes, changed mental status, vertigo, abdominal pain, unusual bowel habits, polydipsia, polyuria, hypotension, and weakness.
 

amylase/lipase increased also included in this section)	grado, se verity j		
 
Patients should be thoroughly evaluated to rule out any alternative etiology (e.g., disease progression including brain metastases, or infections).
 

			
 
Depending on the suspected endocrinopathy, monitor and evaluate thyroid function tests: TSH, free T3 and free T4 and other relevant endocrine and related labs (e.g., blood glucose and ketone levels, HgA1c).
 

			
 
For modest asymptomatic elevations in serum amylase and lipase, corticosteroid treatment is not indicated as
 

		
 
long as there are no other signs or symptoms of pancreatic inflammation.
 
If a patient experiences an AE that is thought to be possibly of autoimmune nature (e.g., thyroiditis, pancreatitis, hypophysitis, or diabetes insipidus), the investigator should send a blood sample for appropriate autoimmune antibody testing.
 

Grade 1	No dose modifications.	
 
For Grade 1 (including those with asymptomatic TSH elevation):
 
Monitor patient with appropriate endocrine function tests.
 

		
 
For suspected hypophysitis/hypopituitarism, consider consultation of an endocrinologist to guide assessment of early-morning ACTH, cortisol, TSH and free T4; also consider gonadotropins, sex hormones, and prolactin levels, as well as cosyntropin stimulation test (though it may not be useful in diagnosing early secondary adrenal insufficiency).
 

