# 5.2 Post-Surgery/Adjuvant Therapy

 Includes weight, BSA, and vital signs (temperature, blood pressure, pulse rate, and). Following the initial presurgery dose, for subsequent doses, the post dose vitals and 1-hour observation period will not be required unless a subject experiences an infusion-related reaction. Vital signs will be measured within an hour prior to start of study drug administration, at 30 minutes during the infusion (± 5 minutes), at the end of infusion (+ 5 minutes). If needed, vital signs will be done at 30 and 60 minutes (± 5 minutes each) post-infusion. If the infusion takes longer than 60 minutes, blood pressure and pulse measurements should follow the principles described here or more frequently if clinically indicated.

 Adjuvant treatment (cycle 1 day 1) will resume approximately 14 days (+/- 7 days) after surgery, once the surgical wound has healed.

 Will be done every other week while on adjuvant treatment.

 Will be done prior to each cycle (monthly) while on adjuvant treatment.

 If patients are unable to start treatment within 21 days of the post-surgical imaging, then repeat imaging with

enhanced MRI or CT scan should be performed prior to initiation of adjuvant therapy. During adjuvant treatment, contrast-enhanced MRI or CT scan will be done approximately every 2 cycles or 8 weeks (prior to each odd cycle). If there is no progression of disease, patients will continue on treatment for up to 24 months. If a patient has disease progression (as defined in section 6.4) or clinical decline and undergoes further surgery but is found to have no pathologic evidence of significant tumor, the patient may then re-start treatment.

-  Thyroid function tests will be done every 2 cycles (approximately every 2 months) during treatment. TSH will be done each time; free T3 and free T4 only if TSH is abnormal.
-  ECGs are required within 1 hour prior to starting study treatment and at least once after the infusion is completed (anywhere from 0-3 hours) on Cycle 1 Day 1, again after approximately 16 weeks on treatment, and at the end of treatment. ECGs may be repeated at any other time point if clinically indicated. ECGs recorded during the treatment phase will be single tracing. Twelve-lead ECGs will be obtained after the subject has been resting in a supine position for at least 5 minutes in each case.

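### The protocol holds drug for asymptomatic Grade 3+ amylase or lipase, but no scheduled laboratory panel names either enzyme

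*Combined protocol and SAP*

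**What the plan says.** The monitoring instruction is in the Pancreatitis paragraph of Section 1.3.3.1: "Subjects should be monitored for signs and symptoms of pancreatitis including Grade 3 or 4 elevations in lipase and/or amylase". The same paragraph gives the action, "For Grade 3 and above asymptomatic amylase or lipase levels hold study drug/regimen", and allows dosing to continue or resume if a full work-up finds no pancreatitis.

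The dose-modification table in Section 4.4 (General Considerations) repeats this hold and work-up for Grade 3 or higher "asymptomatic amylase or lipase levels". The Endocrinopathy row of that table also expects such values to be seen: "For modest asymptomatic elevations in serum amylase and lipase, corticosteroid treatment is not indicated", provided there is no other sign of pancreatic inflammation.

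The schedules are in Sections 5.1 and 5.2. Before surgery, footnote 9 lists the chemistries: "Chemistries should include electrolytes, calcium, , albumin, alkaline phosphatase, bilirubin (total), SGPT(ALT), SGOT(AST), serum creatinine, and BUN". Magnesium and phosphorus have a separate row. After surgery, the table has a row called "Comprehensive Chemistry Panel" with no analyte list. Thyroid testing has its own timing: "Thyroid function tests will be done every 2 cycles (approximately every 2 months) during treatment".

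**The concern.** The hold rule is written for patients who have no symptoms. Such a patient can meet the rule only if the enzyme is measured, and nothing in the schedule says that it will be. Section 1.3.3.1 itself describes immune-mediated pancreatitis as typically showing first as a symptom-free rise in these enzymes. Section 1.3.3.1 also calls it an important potential risk, above all with the combination given in Arm 3, and Section 7.2.4 lists it among the adverse events of special interest.

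Two things are at stake. A patient with an asymptomatic Grade 3 or 4 value could be redosed when the protocol calls for a hold and work-up. And the number, frequency and severity of adverse events is a secondary endpoint (Section 2.2.1). For these two laboratory events the counts would partly reflect who happened to be tested, and in an open-label trial the readiness to test could differ between arms.

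**Working it through.** **Document check.** The plan states no figure on this point, so there is none to reproduce. The check sets each laboratory-defined toxicity against the schedule.

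| Toxicity with a laboratory-based action in Section 4.4 | Scheduled test |
|---|---|
| Hepatitis (AST, ALT, bilirubin) | Named in 5.1 footnote 9 |
| Renal dysfunction (creatinine) | Named in 5.1 footnote 9 |
| Thyroid dysfunction | Thyroid tests at baseline (5.1); TSH every 2 cycles (5.2 footnote 6) |
| Asymptomatic amylase or lipase, Grade 3 or above | None named in any row or footnote of 5.1 or 5.2 |

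The scheduled toxicity assessments would pick up symptomatic pancreatitis. They would not pick up the state that the hold rule describes. The protocol permits testing on suspicion, but for an asymptomatic patient there is usually nothing to suspect.

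**Scale.** The inputs are:

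- Rate: treatment-related Grade 3+ increased lipase in 5.9% of 102 NSCLC patients on the combination (Section 1.4.2).
- Patients in Arm 3: 10 evaluable (target) to 15 (accrual cap, Section 3.0). Every dosed patient is evaluable for toxicity (Section 4.4).
- Formulas: P(at least one) = 1 − (1 − p)^n; expected events = n × p.

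| p | n | Expected events | P(at least one) |
|---|---|---|---|
| 0.059 | 10 | 10 × 0.059 = 0.59 | 1 − 0.941^10 = 0.456 |
| 0.059 | 15 | 15 × 0.059 = 0.89 | 1 − 0.941^15 = 0.598 |
| 0.0295 (assumed half rate) | 10 | 10 × 0.0295 = 0.30 | 1 − 0.9705^10 = 0.259 |
| 0.0295 (assumed half rate) | 15 | 15 × 0.0295 = 0.44 | 1 − 0.9705^15 = 0.362 |

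The half rate is an assumption to show the range; it is not in the documents. All rows count every Grade 3+ lipase event, symptomatic or not. The asymptomatic share, which is what the schedule would miss, is not reported.

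**The case against.** The best defence is that Section 4.4 says what to do if a value is found and does not order screening. It is a sponsor guideline block with material irrelevant to this trial, such as paediatric and hepatocellular carcinoma guidance. Other symptom-free findings in it, such as troponin changes or radiographic pneumonitis, have no scheduled test either. The one monitoring sentence is in a background section and gives no frequency. The panels are also not closed: footnote 9 says what the chemistries should include, and the Section 5.2 panel is undefined, so a site may already be running the enzymes.

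Part of this stands. The documents show that the enzymes are not named, not that they are never measured. But the comparison with troponin and chest imaging is weak, because the protocol has no comparable instruction to monitor for those symptom-free findings, whereas it does name Grade 3 or 4 enzyme elevations. Magnesium and phosphorus also show that this protocol gives an extra analyte its own row when it wants one.

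The harm is also limited, and that stands. If work-up finds no pancreatitis, dosing may resume, so a missed value changes treatment beyond the work-up period only for patients whose work-up would have shown pancreatitis. The documents give no rate for that group. The 5.9% pools cohorts at tremelimumab 3 and 10 mg/kg, while 75 mg here corresponds to about 1 mg/kg. The dose-limiting enzyme event in that study occurred at 3 mg/kg. For MEDI4736 alone, the Grade 3+ events above 1% in 393 patients (Section 1.3.3) include neither enzyme. These points lower the expected count; they do not supply the missing test.

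**Conclusion.** The concern holds. The protocol asks for monitoring of Grade 3 or 4 amylase and lipase values and orders a hold for asymptomatic ones, yet schedules no named test that would reveal them. The omission is certain from the text; its consequence is less so. As an upper guide for Arm 3, the chance of at least one Grade 3+ lipase event is 0.46 to 0.60 at the reported rate, and 0.26 to 0.36 at an assumed half of it. This rests on carrying over an NSCLC rate that includes higher doses and both symptomatic and asymptomatic cases. The effect is on patient safety and on the descriptive adverse-event summary. The sample size, the primary T-cell endpoint and its analysis are untouched. It should be fixed, because the plan cannot reliably trigger its own hold rule and the remedy is cheap.

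**What to change.** Add amylase and lipase to footnote 9 of Section 5.1, itemise the Section 5.2 chemistry panel and include both enzymes there. Test at baseline and at the existing chemistry draws during treatment. Leave the hold rule as it is.

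The cost is a schedule amendment and two more assays on blood already drawn. Some incidental asymptomatic elevations will need the work-up that Section 4.4 already prescribes.

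One limit remains. Adjuvant chemistry is drawn on Day 1 of each cycle, while MEDI4736 is also given on Day 15 in Arms 2 and 3, so the Day 15 dose would have no scheduled enzyme result of its own. The scheduled liver tests have the same limit.
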